### Experimental Design and Methods

**Participants:** Eighty TBI subjects will be recruited for this study, all having suffered mild or moderate TBI (mmTBI, as defined before) at least 3 months prior to study enrollment, but not more than 15 years prior to enrollment. 80 age- and sex-matched healthy controls will be recruited. All participants will be 18-55 years of age. We will expect to screen approximately 120 patients with mmTBI in order to reach our goal of 80 TBI subjects. The experimental pre-post, double-blind design is graphically displayed. It includes randomization of TBI patients to either a left-sided active transcranial direct current stimulation (tDCS) protocol, or sham treatment group to foster isolation and identification of any tDCS treatment effects. To enhance our statistical power to identify predictors of treatment response in mmTBI patients, 40 TBI subjects and 40 controls will be assigned to each group: left-sham and left-active.

**Recruitment:** Recruitment primarily will be through the UNM Hospital Emergency Department (ED) (the only Level 1 trauma center in New Mexico). The UNM Health Sciences Center (HSC) Clinical and Translational Science Center (CTSC) Participant Recruitment Service (PRS) for Clinical Research will monitor ED intake records for patients who meet criteria once released from the hospital, then notify the study team of these cases. A second means of recruitment will involve direct referrals from UNM and non-UNM ED physicians and/or referrals from any clinic in the Albuquerque metropolitan area, via the distribution of flyers and calls to clinical directors to publicize the study. A third means of recruitment will involve information listed on the UNM CBRR and MRN websites, and posted flyers.

**PROTOCOL TITLE:** Transcranial direct current stimulation for treatment of deficits after traumatic brain injury.

[figure not shown]

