Subjects who meet initial criteria for inclusion will be contacted by a member of the research team and invited to enroll in the study. Interested patients will be invited to the offices of the Center for Brain Recovery and Repair clinical core for formal screening procedures. A brief structured interview will be administered along with the NSI. If potential participants do not meet study criteria, they will be thanked for their time and identifying information recorded for future reference. Subjects with a legally authorized representative (LAR) will be excluded from the study, and all participants will be screened for LAR. All participants will be adults (ages 18-55), and all participants will consent for themselves. Although participants will be recruited from referral or from emergency department (or other) records, no participant will be enrolled in the study without being given sufficient opportunity to consider whether or not to participate. In most cases, they will undergo multiple interactions with study personnel over the course of days, and during each they will have the opportunity to ask questions and discuss their decision to participate. They will have multiple opportunities to reconsider any decisions during the screening and consent process, minimizing the possibility of coercion or undue influence by the researchers. If potential participants successfully meet basic study criteria, they will be invited to undergo consent procedures and enrolled in the study. All participants will be fluent in English, and the information contained in the consent form will be discussed with them in addition to their having a written description of the study in the form, to assure that they truly understand the study procedures.

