Randomization will occur at time of consenting. The study coordinator who consented the patient will use a coin-tossing procedure to determine whether the subject is assigned to the active group (group 1) or control group (group 2). Modifications will be made as necessary toward the end of enrollment to ensure equal group size and balanced distribution of demographic variables such as age and gender. The study coordinator will not be blinded to group assignment, and with the assistance of the Clinical Core, will program the TDCS devices to deliver active or sham stimulation depending on which group the subject has been assigned. However, the coordinator will not be involved in performing any stimulation procedures. The study technician and principle investigator, who will be responsible for administering the stimulation, will not be aware of which group receives active versus control, and will thus be blinded, as the TDCS device will only display the group number (1 or 2).

Once group membership is determined, individual participants may undergo demographic data collection, neuropsychological assessments and tDCS treatment sessions. They may also undergo EEG and/or MRI. Direct identifiers of participants will be maintained on a separate database that will be stored behind locked doors, in a locked filing cabinet in a secure area of the Clinical Core.

**Demographic Data:** As part of the initial assessment, basic demographic data regarding the subject may be noted down, including age, gender, socioeconomic status, educational attainment, handedness, use of common stimulants such as caffeine, and brain injury severity. They may also be asked if they are willing to allow their medical record to be accessed, for the purposes of confirming details about any TBI as well as obtaining results of neuroimaging studies done at the time of injury or afterward. This will include medical, surgical, neurological and psychiatric history, results of lab tests, brain scans, electroencephalography tests, medication lists, information from doctor's visits and hospital visits.

**Neuropsychological testing procedures:** All neuropsychological testing will be administered in the Center for Brain Recovery and Repair Core by trained study personnel under direct supervision of core directors, clinical neuropsychologists Drs. [name], [name], or the PI. The primary dependent outcome variables to be studied are the three composite scores generated by

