Statistical analyses will utilize the CTSC Biostatistics core. Power analyses and statistical analysis strategy were determined with our statistician [name], who will continue to provide recommendations and support throughout the project. Sufficient group sizes were determined on the basis of data derived from preliminary studies. Clark and colleagues found an effect size of Cohen's  $d = 1.2$  for tDCS to induce improvements in cognition. For our power calculations we will assume a more conservative effect size of  $d = 0.7$  which is consistent with a recent meta-analysis of tDCS effect sizes. With 40 tDCS treatment patients compared to 40 sham patients and an effect size of 0.7, we have 80% power to detect effects of active versus sham treatment in a two-sample t-test. Power in the linear mixed model analysis should be superior that that of the t-test. For Aim 1.1, the central analyses evaluate group (active vs. sham) differences in the EEG data and on the three Examiner composite variables across the three initial time points (before, immediately after, and 1 month after tDCS stimulation protocol). To test this hypothesis, three separate linear mixed models analyses will be performed using the three Examiner composite scores (Fluency, Cognitive Control, Working Memory) as dependent variables. In each analysis, we will incorporate three covariates that may predict variation in learning (severity: mild vs. moderate, premorbid intelligence: WTAR score, and symptom burden: NSI). This will allow us to determine predictors of treatment response (Specific Aim 1.3). Sex, ethnicity, and age will also be entered into the statistical model. The effects of these covariates will be estimated by constructing appropriate contrasts in model effects. A similar set of analyses will evaluate group differences on the variables assessed in our long-term oral/phone follow-up (five data points: (1) before tDCS, (2) immediately after tDCS, (3) 1 month post-tDCS, (4) 6 months, and (5) 1 year) for Aim 1.2. For these analyses dependent variables will be the total cognitive items score of the NSI and the PROMIS-29 profile total score). Significant effects will be followed up with more fine-grained analysis of the components of composite scores. The use of linear mixed-models minimizes the adverse impact of a missing data point, which may well occur in a longitudinal clinical study such as this. Expected attrition will be taken into account with an intention-to-treat analysis. Missing data patterns will be analyzed to assess the extent to which they are informative (in contrast to missing at random), and analyses adjusted accordingly. All EEG data will undergo standard preprocessing (e.g. motion correction, spatial normalization) and quality control prior to statistical modeling. Depending on the specific question of the study, data may be analyzed using the general linear model, independent components analysis, machine learning techniques, or a variety of other standard approaches for neuroimaging data.

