multiple opportunities to reconsider any decisions during the screening and consent process, minimizing the possibility of coercion or undue influence by the researchers. If potential participants successfully meet basic study criteria, they will be invited to undergo consent procedures and enrolled in the study. All participants will be fluent in English, and the information contained in the consent form will be discussed with them in addition to their having a written description of the study in the form, to assure that they truly understand the study procedures.

A modified repeated fair coin-tossing randomization procedure will determine group assignment, and modifications will be made as necessary toward the end of enrollment to ensure equal group size. Randomization will occur at time of consenting. The study coordinator who consented the patient will use a coin-tossing procedure to determine whether the subject is assigned to the active group (group 1) or control group (group 2). Modifications will be made as necessary toward the end of enrollment to ensure equal group size and balanced distribution of demographic variables such as age and gender. The study coordinator will not be blinded to group assignment, and with the assistance of the Clinical Core, will program the TDCS devices to deliver active or sham stimulation depending on which group the subject has been assigned. However, the coordinator will not be involved in performing any stimulation procedures. The study technician and principle investigator, who will be responsible for administering the stimulation, will not be aware of which group receives active versus control, and will thus be blinded, as the TDCS device will only display the group number (1 or 2).

Once group membership is determined, individual participants will be scheduled for demographic data collection, neuropsychological assessments, EEG, and tDCS treatment sessions. Direct identifiers of participants will be maintained on a separate database that will be stored behind locked doors, in a locked filing cabinet in a secure area of the Clinical Core.

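### Arms are assigned by an unblinded consenter's coin toss, with undefined late changes to even up the groups: late assignments become knowable or choosable, and no assignment can be verified afterwards

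*Combined protocol and SAP*

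**What the plan says.** Section 10 (Study Procedures, Experimental Design and Methods for Aim 1.1) places randomization at consent: "The study coordinator who consented the patient will use a coin-tossing procedure". Heads or tails decides group 1 (active) or group 2 (control). On the same person it says "The study coordinator will not be blinded to group assignment", and that this person, with help from the Clinical Core, programs the device. It then provides: "Modifications will be made as necessary toward the end of enrollment to ensure equal group size and balanced distribution of demographic variables", with age and gender as examples.

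Section 18 (Recruitment Methods) repeats the procedure. It opens with "A modified repeated fair coin-tossing randomization procedure will determine group assignment" and gives the override twice, the first time as "modifications will be made as necessary toward the end of enrollment to ensure equal group size". The word modified is not defined.

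Other relevant statements:

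- **Target allocation (Section 10, Participants):** "40 TBI subjects and 40 controls will be assigned to each group: left-sham and left-active".
- **Contact before assignment (Section 10):** a structured interview and the NSI at screening, and "In most cases, they will undergo multiple interactions with study personnel over the course of days".
- **Double-blind paragraph (Section 10):** the stimulator itself is said to do the randomizing and to keep a record that can be downloaded later.
- **Section 23 (Consent Process):** the PI, the coordinator or a research assistant may take consent.
- **Section 11 (Data Analysis):** severity, WTAR, NSI, sex, ethnicity and age enter the mixed models.

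**The concern.** A randomized comparison needs assignments that nobody involved in enrolment can foresee or choose. Two features work against that.

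Early on, an honest toss cannot be foreseen, but nothing described would let anyone confirm that a toss happened, happened once, and was followed. The person who recruited the patient sees the result and programs the arm.

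Late on, equalizing the arms makes assignments predictable to anyone who knows the running count, and balancing age and gender without an algorithm means that somebody picks the arm. By then study personnel have met the patient, in most cases several times.

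The safeguards in the plan do not answer this. Keeping the coordinator away from stimulation, and showing the technician and PI only a group number, concern blinding after assignment, not concealment before it. Concealment that was absent at enrolment cannot be restored at analysis.

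**Working it through.** **1. The plan's own figure.** Section 11 states: "With 40 tDCS treatment patients compared to 40 sham patients and an effect size of 0.7, we have 80% power". No alpha is given. With a two-sample t-test, noncentrality = d × √(n₁n₂/(n₁+n₂)) = 0.7 × √(1600/80) = 3.13 on 78 df. At an assumed two-sided alpha of 0.05 the power is 87.1%, not 80%. About 80% appears with a two-sided alpha of 0.025 (79.9%) or with 33 evaluable per arm (80.0%); neither is stated. The stated figure is conservative at 0.05 and does not affect this point.

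**2. How often the override is needed.** P(exactly 40/40) = C(80,40)/2⁸⁰ = 0.0889. So about 91% of fair-coin sequences miss the stated split.

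**3. How many late assignments become certain.** Assume the coin is tossed until one arm reaches 40 and the other is then filled. P(forced tail = 80 − m) = 2·C(m−1,39)/2ᵐ, for m = 40 to 79. The mean is 80 × 0.0889 = 7.1 and the median 6. The tail is 8 or more in 41% of sequences and 16 or more in 6%. If one sequence covered all 160 participants, the mean would be 10.1.

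**4. What the override buys.** Power at d = 0.7, assumed two-sided alpha 0.05:

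| Split | Power |
|---|---|
| 40/40 | 87.1% |
| 35/45 | 86.6% |
| 31/49 | 85.4% |
| Averaged over fair-coin outcomes | 86.7% |

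The average gain from forcing 40/40 is 87.1 − 86.7 = 0.4 points. A fair coin is at least as balanced as 31/49 in 96.7% of sequences.

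**5. How large the bias might be (illustration only).** The extent of the changes is not stated, so the bias cannot be bounded. Assume no true effect, 40 per arm, and an impression (cue) correlated 0.3, 0.5 or 0.7 with outcome. Partial adjustment means a covariate that carries half of the cue's variance. Type I error, nominal 5%:

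| Scenario | Partial adjustment | Unadjusted |
|---|---|---|
| Fill rule, better or worse of two candidates consented in the forced tail | 5.2 / 5.2 / 5.5% | 5.3 / 5.8 / 6.6% |
| Last 8 steered one at a time | 5.1 / 5.2 / 5.4% | 5.3 / 5.7 / 6.5% |
| Last 16 steered one at a time | 5.3 / 6.0 / 7.6% | 6.5 / 8.9 / 13.1% |

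The adjusted column is closer to the planned analysis.

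**6. Which replacement is hardest to guess.** For an observer who sees every past arm among 80:

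| Scheme | Assignments certain | Best guess right |
|---|---|---|
| Coin, then fill | 7.1 | (7.1 + 72.9/2)/80 = 54.4% |
| One 40/40 permutation | 2·40/41 = 1.95 | [40 + (1/0.0889 − 1)/2]/80 = 56.4% |
| Hidden random blocks of 4, 6, 8 (simulated) | 1.9 | 67.9% |

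**7. Statements side by side.** The double-blind paragraph has the machine randomizing; the randomization paragraph and Section 18 have a coin decide and the coordinator program the result. If the coin governs, the device log shows what was delivered, not whether a toss was repeated or an arm chosen. Section 23 lets the PI take consent, yet in Sections 10 and 18 whoever consents also assigns unblinded, while the PI is meant to be blinded.

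**The case against.** The strongest reply is that the stated purpose is benign. Equal size and balance on age and gender, with both in the model, resembles informal minimization adjusted at analysis. Harm requires someone to act on other prognostic impressions, and little is on file at assignment: an interview and the NSI, which is itself a covariate. Neuropsychological testing comes after assignment. Those who meet criteria are to be invited and enrolled, so a pool from which to consent selectively is not described. The 7.6% needs all of the last 16 patients steered at correlation 0.7, while a fill tail reaches 16 in only 6% of sequences. The 13.1% belongs to an unadjusted test, which is not the planned efficacy analysis.

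Most of this stands, and it limits the claim about size. It does not supply a rule, a decision-maker or a record, and covariates cannot remove selection on impressions that nobody measured.

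A reader might also infer three things that the documents do not support:

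- **That the coordinator makes the late changes.** The sentences are passive and name nobody. The undefined decision-maker is part of the defect, but the text does not assign the role.
- **That Section 3 also conflicts with the coin toss.** Its pre-programmed stimulator is compatible with a coordinator who programs the assigned arm.
- **That permuted blocks are the obvious remedy.** For a person who consents, programs and sees past arms, blocks are easier to guess than one permutation (68% against 56%).

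**Conclusion.** The concern holds. As written, late assignments can be known or chosen, and no assignment can be verified afterwards. The size of the exposure, about 7 certain TBI assignments on average, rests on the assumed fill rule; the 8.9% rests only on a fair coin and the stated 40/40.

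It would be tempting to conclude that the active-versus-sham result would be seriously biased. The documents do not support that. In the assumed scenarios with partial adjustment, type I error is about 5.1-5.5% for the fill rule or the last 8 patients steered, and up to 7.6% for the last 16. Those correlations and the half-captured cue are assumptions, and the true extent of the changes is unknown.

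The plan accepts this exposure for about 0.4 points of power and for balance on two variables that it already adjusts for. Correcting it is a cheap improvement.

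**What to change.** Replace the coin toss and delete the three statements about late changes (one in Section 10, two in Section 18). Suggested text:

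> The CTSC Biostatistics core will generate one random permutation of 40 active and 40 sham assignments for each cohort (TBI, healthy). The list is concealed from everyone who consents participants. Each assignment is released and logged only after consent and eligibility are final.

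Use random, undisclosed block sizes only if someone who does not consent participants programs the device.

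If the sponsor wants to keep forced balance on age and sex, it should use a pre-specified algorithm with a random element, run by the biostatistics core, rather than ad hoc changes.

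Reword the double-blind paragraph of Section 10 to say that the device delivers and logs the assigned arm. Align Sections 10, 18 and 23 on who takes consent and who assigns.

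**Cost:** one amendment and two short lists from a core already engaged; sample size, visits and outcomes do not change. Each release must fit before a first session that may fall on the day of assessment. Exact balance on age and sex is not forced, although both remain covariates. A coordinator who still programs the device will see past arms, but under the permutation only about 2 of 80 assignments per cohort become certain, against about 7 under the assumed fill rule.

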### 3. Study Design

This study is a randomized placebo-controlled clinical trial. Investigators will be blinded to the type of stimulation given (sham versus active) through use of a computer-assisted pre-programmed tDCS stimulator. Subjects will be blinded to sham versus active through the use of low-current (up to 0.2 mA) sham stimulation, which provides a tactile sensation similar to active 2.0 mA stimulation. Ramping up and down the current at the beginning of stimulation also prevents subjects from distinguishing sham from active. The duration of an individual subject's participation in the research may range up to 1 year. The duration anticipated to enroll all subjects is 3 to 4 years. The expected duration for the investigators to complete the study (complete analysis) is 5 years.

**PROTOCOL TITLE:** Transcranial direct current stimulation for treatment of deficits after traumatic brain injury.

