below the deltoid. Current for the treatment condition will be applied at 2.0 mA for a total delivered charge of 60 mA-min.

*Safety of stimulation.* During tDCS application, subjects will describe physical sensations such as tingling or itching using a 10-point anchored Likert scale. Administration of tDCS will be stopped immediately if subjects report a 7 or above for discomfort, or if subjects wish to stop at any time. Subjects will also have their mood, energy, pain, and arousal levels assessed using visual analog 10-point scales. These checks will occur every ten minutes during the stimulation session.

*Double blind design and sham treatment:* The sham stimulation (control) group will receive up to 0.2 mA current for 30 minutes each session, with an initial ramping up and down of stimulation to mimic active stimulation. The sham current is used as a control condition, rather than the absence of stimulation, to equate aspects of the procedure (preparation and application of electrodes, attachment with adhesive strips, etc.), and to give the participant a degree of physical sensation that is somewhat similar to that of the 2.0 mA stimulation group while remaining well below the level sufficient to affect brain function and behavior. To accomplish a double blind, the tDCS machine is programmed to randomize sham versus active stimulation and keeps track of the stimulation protocol for later downloading.

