
## 12. Provisions to Monitor the Data to Ensure the Safety of Subjects

Data safety and monitoring will be carried out to ensure and maintain the scientific integrity of this project and to protect the safety of our participants. Safety monitoring is the process during the study that involves review of accumulated outcome data for groups of subjects to determine if any of the procedures practiced should be altered or stopped. Ultimately, the PI ([name]) will be responsible for monitoring the safety of the study and complying with the reporting requirements. An independent Data Safety and Monitoring Board (DSMB) will review the study data on a quarterly basis with the PI to ensure participant safety. The DSMB for this study will be composed of [name], the medical director of the Electroconvulsive Therapy Service at UNM, and [name], staff epileptologist of the Epilepsy Monitoring Unit at UNM. Their experience in assuring safety of brain stimulation therapies and seizure monitoring protocols make them ideally suited to serving on this project's DSMB. Continuous, close monitoring of participant safety will include prompt and frequent reporting of safety data (i.e., adverse/serious adverse events) to the

**PROTOCOL TITLE:** Transcranial direct current stimulation for treatment of deficits after traumatic brain injury.

DMSB, the University of New Mexico Health Sciences Center Institutional Review Board (UNMHSC IRB) and/or appropriate NIH staff with oversight responsibility. The PI will provide a summary of the safe conduct of the study to NIH on an annual basis as part of the progress report. All AEs occurring during the course of the study will be collected, documented, and reported to the UNMHSC IRB.

The review of data may result in early termination of the study, amendment to the protocol, or changes to the data collection plan or study forms if it appears that there are adverse events occurring at a rate significantly greater than that found in similar tDCS studies involving subjects with neurological disorders (ie. stroke). Should the protocol or data collection plans or study forms be amended as a result of data review, the IRB will be notified and the amendment approved prior to study amendment implementation. In addition, the participants will be notified of any significant new findings that develop during the course of research that may affect their wish to continue participation in the study.

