## **28. Community-Based Participatory Research NA**

## **29. Research Involving American Indian/Native Populations NA**

## **30. Transnational Research NA**

## **31. Drugs or Devices**

A NeuroConn ([www.neuroconn.de](http://www.neuroconn.de)) tDCS machine will be used to administer tDCS current. Square-shaped, 11 cm^2 saline water (15mM) solution-soaked sponge electrodes, held by a rubber casing, are applied to the scalp using elastic bandage material. The anode will be placed on the scalp over the F3 target location and the cathode placed on the right upper arm below the deltoid. Current for the treatment condition will be applied at 2.0 mA for a total delivered charge of 60 mA-min.

**PROTOCOL TITLE:** Transcranial direct current stimulation for treatment of deficits after traumatic brain injury.

[name] as well as the research coordinator and technician who will be applying tDCS will undergo training with [name], who is a national expert in tDCS and has published extensively on the safe and efficacious use of tDCS for cognitive enhancement. [name] will also undergo training with his external mentor [name], who is also a national expert on tDCS safety and mechanisms of action.

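### Operators are masked by a group number that the protocol itself decodes, and allocation is described in two ways that do not match

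*Combined protocol and SAP*

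**What the plan says.** Section 3 (Study Design) makes investigator blinding a design feature: "Investigators will be blinded to the type of stimulation given (sham versus active) through use of a computer-assisted pre-programmed tDCS stimulator".

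Section 10 (Experimental Design and Methods) gives the mechanism, and section 18 (Recruitment Methods) repeats it. At consent the study coordinator tosses a coin to decide "whether the subject is assigned to the active group (group 1) or control group (group 2". The coordinator is unblinded and, with help from the Clinical Core, programs the device to match. Section 18 adds that "the coordinator will not be involved in performing any stimulation procedures". The technician and the PI administer the stimulation and are said to be unaware of the arm, "as the TDCS device will only display the group number (1 or 2".

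The section 10 paragraph on double-blind design and sham treatment explains the blind differently: "the tDCS machine is programmed to randomize sham versus active stimulation and keeps track of the stimulation protocol for later downloading".

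On numbers, section 10 states that "40 TBI subjects and 40 controls will be assigned to each group: left-sham and left-active". It does not say how the healthy controls' devices are labelled.

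**The concern.** The only reason given for operator blinding is that the operator sees a number and not the name of the arm. The protocol prints what that number means in the same paragraph, so anyone who has read sections 10 or 18 can turn the display into the arm. A code with only two fixed values is also fragile when the key is hidden: one participant unmasked for any reason unmasks everyone else.

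The second problem is that the reader cannot tell how allocation works. Either the coordinator tosses a coin and the device carries out the result, or the device randomizes. These differ in who knows the assignment and when, so they imply different safeguards.

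What is at stake is the trial's description as double-blind. An operator who knows the arm may influence how sessions are conducted. If the same person also rates outcomes, a clinician-rated scale such as the HAM-D is open to rater expectation. Blinding lost during delivery or rating cannot be restored at analysis.

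**Working it through.** The plan has no figure of its own to reproduce here. The check compares the text and then counts what one unmasking exposes.

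**Step 1. The label.** Sections 10 and 18 both map group 1 to active and group 2 to control, and both say the device displays that same 1 or 2. No section says the displayed number is scrambled, that the key is restricted, or that operators work from a masked version of the protocol. The lack of awareness is asserted without a safeguard.

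**Step 2. Who can read it.** Section 12 says the PI "will be responsible for monitoring the safety of the study and complying with the reporting requirements", so the PI has to know the protocol. Section 7 (Resources Available) has technicians, coordinators and investigators attending weekly meetings about the protocol. The documents do not say whether technicians see the key.

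**Step 3. Allocation.** In sections 10 and 18 a person allocates and then programs the device. In the sham paragraph of section 10 the machine randomizes. Section 3 says only that the stimulator is pre-programmed, which fits either account. The sham paragraph does not withdraw the displayed group number.

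**Step 4. Operators and raters.**
- Section 7 gives neuropsychological batteries to Core psychometricians. Section 10 places the HAM-D in that battery at baseline, immediately after stimulation and at 1 month.
- No section bars an operator from testing. Section 7 has technicians assisting with assessment and scoring, section 10 lets the PI supervise testing, and section 14 has data collected by the PI or research assistants. The Clinical Core, which tests, also helps program the devices.
- Aim 2.2 repeats the depression scales by telephone at 6 months and 1 year and names no rater. The parallel NSI and PROMIS-29 calls in Aim 1.2 are made by the research team.
- Section 31 refers to "the research coordinator and technician who will be applying tDCS will undergo training". This can be read as the coordinator applying stimulation, against sections 10 and 18. It is an ambiguity and is not counted as a contradiction.

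**Step 5. Counts.** Inputs: 80 TBI participants and 80 controls, 40 of each per arm, and up to 10 sessions each (section 10).

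| Quantity | Arithmetic | Result |
|---|---|---|
| Sessions, TBI only | 80 × 10 | up to 800 |
| Sessions, controls sharing the code | 160 × 10 | up to 1,600 |
| Revealed by one unmasking, two codes | the other code follows by elimination | 80/80, or 160/160 if shared |
| Revealed directly, 4 codes per arm used equally | 40/4 = 10; 10/80 | 12.5% (if shared, 80/4 = 20; 20/160 = 12.5%) |
| Revealed, unique codes | 1/80 | 1.25% |
| Post-stimulation HAM-D, TBI | 4 × 80 | at most 320 |
| of which in the battery (immediately after, 1 month) | 2 × 80 | 160 |
| of which by telephone, no named rater (6 months, 1 year) | 2 × 80 | 160 |
| Post-stimulation EXAMINER, TBI | 2 × 80 | at most 160 |

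These are upper bounds before attrition on what could be exposed. They do not count biased ratings.

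**The case against.** The strongest reply is that nothing shows the trial's results would be affected. Participants are blinded separately, by low-current sham and ramping, and that is not in question. The primary endpoint, the EXAMINER, is a test battery given by psychometricians who are not the named operators. The main exposure is then one clinician-rated secondary endpoint, and only if an operator also rates. The protocol also states outright that operators will not know which group is which. The remark that the machine randomizes may be loose wording for a device programmed to deliver an assigned condition. The head-counts would follow from any two-label scheme and do not measure bias.

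Much of this stands. No bias is demonstrated, the EXAMINER is less exposed than the HAM-D, technicians' access to the key is unknown, and the counts are ceilings. It does not remove the defect. A statement that operators will be unaware, supported only by a label the document decodes, is not a safeguard, and for the PI it is hard to credit. If the word randomize is loose, no section says so, and the text still needs reconciling. The psychometrician arrangement does not cover the telephone HAM-D ratings, and no rule keeps operators out of assessment.

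**Conclusion.** The concern holds. As written, operator blinding (sections 10 and 18) and investigator blinding (section 3) are not secured by the mechanism described, and section 10 gives two accounts of allocation that do not match. One unmasking under the present code reveals 80 of 80 TBI participants. The figure of 160 of 160 assumes that healthy controls share the code, which the documents do not settle. Up to 320 post-stimulation HAM-D ratings in TBI participants could be exposed, 160 of them with no named rater.

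This is a risk to the validity of the blind; it is not evidence of bias. It still has to be corrected, because the double-blind claim rests on this mechanism and the repair is inexpensive. The wording in section 31 and the separation of operators from raters are points to clarify and do not carry the conclusion.

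**What to change.** 1. Replace the group number with participant-specific device codes. If the device cannot support these, use several codes per arm, for example 4. The unblinded coordinator or CTSC Biostatistics holds the list linking codes to arms. Remove the statement of which group is active from every document operators see, and state how healthy controls' devices are coded.
2. Reconcile the sham paragraph of section 10 with the allocation text in sections 10 and 18, so that one allocation and blinding mechanism is described.
3. Clarify in section 31 that the unblinded coordinator does not apply stimulation, as sections 10 and 18 already say. State that whoever allocates or programs devices does not test participants, and that the HAM-D rater, including for the 6-month and 1-year calls, does not deliver stimulation. Existing staff can cover this.

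The cost is protocol wording, device-code set-up, a check of how many codes the device supports, and minor scheduling to keep the HAM-D rater separate from the operators. Sample size, visit schedule, stimulation and the Year 2 preliminary analysis are unchanged.
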